4.9. Pharmacodynamic and Biomarker Variables

Biomarkers to be analyzed in this study are:

- TARC
- Total serum IgE
- hsCRP
- Serum amyloid A (SAA)
- Lactate dehydrogenase (LDH) [which will be measured as part of the blood chemistry]

Serum samples for measurements of biomarkers to study the PD activity of study treatments in AD patients will be collected at time points according to [Table 1](#).

5. STATISTICAL METHODS

For continuous variables, descriptive statistics will include the following: the number of patients reflected in the calculation (n), mean, median, standard deviation, first quartile (Q1), third quartile (Q3), minimum, and maximum.

For categorical or ordinal data, frequencies and percentages will be displayed for each category.

All data will be summarized by treatment group.

The safety data collected during the COVID-19 pandemic will be analyzed separately for the impacted patients, if applicable.

5.1. Demographics and Baseline Characteristics

Demographics and baseline characteristics variables (see Section 4.1) will be summarized by treatment group for FAS. Listing of demographics and baseline characteristics will be presented.

5.2. Medical and AD History

Medical history will be summarized by primary SOC and PT for each treatment group for SAF. The table will be sorted by decreasing frequency of SOC followed by PT based on the overall incidence across treatment groups. Medical history will be listed.

Information on conditions related to AD includes diagnosis of AD and AD treatment history, asthma, allergic conjunctivitis, allergic rhinitis, chronic rhinosinusitis, nasal polyps, eosinophilic esophagitis, food allergy hives and other allergies due to medications, animals, plants, mold, etc. History of eye/conjunctival disorder will also be summarized.

5.3. Prior/concomitant Medications and Procedures

Number and proportion of patients taking prior/concomitant medications will be summarized by treatment group for SAF, sorted by decreasing frequency of ATC Level 2 and ATC level 4 based on the incidence in the REGN3500 treatment group. Patients will be counted only once for each medication class (ATC level 2 and 4) linked to the medication. The prior systemic corticosteroid, immunosuppressant, phototherapy use and the concomitant topical steroid eye drops or cyclosporine eye drops will be summarized similarly.

Number and proportion of patients undergoing a prior/concomitant procedure(s) will be summarized, sorted by decreasing frequency of SOC and PT based on the incidence in the REGN3500 treatment group. Patients will be counted only once for each SOC and PT linked to the procedure.

The compliance of moisturizers (emollients) used from 7 days before the baseline visit to end of study, which is defined as the (number of days moisturizers used during the period) / (number of days within the period) x 100%, will be summarized by treatment group.

Descriptive statistics or listings will be provided for the prior and concomitant medications and procedures for the patients impacted by COVID-19 pandemic as well as for three periods (pre-, during-, post-COVID-19 periods), if applicable.

5.4. Rescue/Prohibited Medications and Procedures

Rescue/prohibited medication and procedures will be summarized by treatment group for SAF and FAS, separately. Number and proportion of patients taking medications and rescue medications will be summarized, sorted by decreasing frequency of ATC level 2 and ATC level 4 based on the incidence in the REGN3500 treatment group. Patients will be counted only once for each medication class (ATC level 2 and 4) linked to the medication.

Number and proportion of patients undergoing prohibited procedures and rescue procedures will be summarized, sorted by decreasing frequency of SOC and PT based on the incidence in the REGN3500 treatment group. Patients will be counted only once for each SOC and PT linked to the procedure.

Prohibited medications will be listed.

Descriptive statistics or listings will be provided for the rescue medications for the patients impacted by COVID-19 pandemic as well as for three periods (pre-, during-, post-COVID-19 periods), if applicable.

5.5. Subject Disposition

The following summaries will be provided:

- The total number of screened patients
- The total number of randomized patients: received a randomization number
- The total number of patients in each analysis set by visit and overall
- The total numbers of patients who completed the study treatment and who discontinued the study treatment with the reason of discontinuation
- The total numbers of patients who completed the study and who discontinued the study with the reason of discontinuation (including COVID-19 related reasons)
- The total number of patients who entered follow-up period

The following listings will be provided:

- Listing of patient disposition including: date of randomization, date of the last visit, received dose, completed study treatment or discontinued, completed study or discontinued
- A listing of patients randomized but not treated, and patients randomized but not treated as randomized
- A listing of patients prematurely discontinued from the treatment or from the study, along with reasons for discontinuation
- A summary table and a listing of protocol deviations will be provided.
- The listing of the protocol deviations for the prohibited treatments will be provided.

5.6. Extent of Study Treatment Exposure and Compliance

5.6.1. Measurement of Compliance

Compliance with study treatment will be calculated for REGN3500 injection by treatment group as follows:

Treatment Compliance =

$$\frac{\text{(Number of study drug injections during exposure period)}}{\text{(Number of planned study drug injections taken during exposure period)}} \times 100\%$$

Summary of study drug administration will include the number of study drug doses administered and treatment compliance. The treatment compliance will be presented by the following specific ranges for each treatment group: <80%, and ≥80%.

Listing of dose administration: including date/time, study day, number of injections, locations of injections, dosing information, and whether or not the total dose is administered for each dose will be presented.

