Target Population:

Male or female adult patients (≥ 18 to 75 years of age) with moderate-to-severe AD whose disease cannot be adequately controlled with topical medications or for whom topical treatments are medically inadvisable (eg, intolerance, other important side effects or safety risks).

Treatment(s)

Study Drug	REGN3500 is supplied in vials as a lyophilized powder for reconstitution and SC administration.
Dose/Route/Schedule:	REGN3500 SC: 300 mg SC every 2 weeks (Q2W), 300 mg SC every 4 weeks (Q4W), 100 mg SC Q4W, or 30 mg SC every 8 weeks (Q8W) from day 1 through week 14
Placebo	Placebo that matches REGN3500 (REGN3500-matching placebo) will be prepared in the same formulation as REGN3500, without the addition of protein, for SC administration.
Route/Schedule:	REGN3500-matching placebo SC administration schedule is driven by the treatment assignment to achieve blinding across treatment groups.
Treatment Regimens:	
REGN3500 300 mg SC Q2W: 2 injections of REGN3500 (300 mg total dose) plus 1 injection of REGN3500-matching placebo administered SC on day 1 and week 8; and 2 injections of REGN3500 (300 mg total dose) administered SC at weeks 2, 4, 6, 10, 12, and 14.
 
REGN3500 300 mg SC Q4W: 2 injections of REGN3500 (300 mg total dose) plus 1 injection of REGN3500-matching placebo administered SC on day 1 and week 8; 2 injections of REGN3500 (300 mg total dose) administered SC at weeks 4 and 12; and 2 injections of REGN3500-matching placebo administered SC at weeks 2, 6, 10, and 14.
 
REGN3500 100 mg SC Q4W: 1 injection of REGN3500 (100 mg total dose) plus 2 injections of REGN3500-matching placebo administered SC on day 1 and week 8; 1 injection of REGN3500 (100 mg total dose) plus 1 injection of REGN3500-matching placebo administered SC at weeks 4 and 12; and 2 injections of REGN3500-matching placebo administered SC at weeks 2, 6, 10, and 14.
 
REGN3500 30 mg SC Q8W: 1 injection of REGN3500 (30 mg total dose) plus 2 injections of REGN3500-matching placebo administered SC on day 1 and week 8; and 2 injections of REGN3500-matching placebo administered SC at weeks 2, 4, 6, 10, 12, and 14.
 
Placebo SC Q2W: 3 injections of REGN3500-matching placebo on day 1 and week 8; and 2 injections of REGN3500-matching placebo administered SC at weeks 2, 4, 6, 10, 12, and 14.

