7. STUDY TREATMENTS

7.1. Investigational and Reference Treatments

REGN3500 is supplied in vials as a lyophilized powder. Each vial is reconstituted with 2.5 mL sterile Water For Injection, resulting in 2.0 mL withdrawable volume of 100 mg/mL REGN3500. Placebo that matches REGN3500 (REGN3500-matching placebo) is prepared in the same formulation as REGN3500 but without the addition of protein (ie, active substance, anti-IL-33 mAb). REGN3500 300 mg (or matching placebo) is administered as one 2.0 mL injection and one 1.0 mL injection, REGN3500 100 mg (or matching placebo) as one 1.0 mL injection, and REGN3500 30 mg (or matching placebo) as one 0.3 mL injection.

Study drug (REGN3500, REGN3500-matching placebo) will be prepared by an unblinded pharmacist (or qualified designee) and administered SC by a blinded study nurse (or other qualified study personnel) on day 1/baseline and then as noted below through week 14. The last dose of study treatment will be administered at week 14. Patients will be monitored at the study site for a minimum of 30 minutes after each administration of study drug, and the monitoring period may be extended up to 2 hours as per country-specific requirements.

Patients will be randomly assigned 1:1:1:1:1 to receive one of the following treatment regimens:

Table 1: Dosing Regimens

Dose Regimen	Injections During Visit	Study Drug Administered	Injection Volume (mL)
Day 1 (Visit 2) and Week 8 (Visit 6)			
REGN3500 300 mg SC Q2W	3	Placebo	0.3
		REGN3500	1.0
		REGN3500	2.0
REGN3500 300 mg SC Q4W	3	Placebo	0.3
		REGN3500	1.0
		REGN3500	2.0
REGN3500 100 mg SC Q4W	3	Placebo	0.3
		REGN3500	1.0
		Placebo	2.0
REGN3500 30 mg SC Q8W	3	REGN3500	0.3
		Placebo	1.0
		Placebo	2.0
Placebo SC Q2W	3	Placebo	0.3
		Placebo	1.0
		Placebo	2.0
Weeks 2 (Visit 3), 6 (Visit 5), 10 (Visit 7), and 14 (Visit 9)			
REGN3500 300 mg SC Q2W	2	REGN3500	1.0
		REGN3500	2.0
REGN3500 300 mg SC Q4W	2	Placebo	1.0
		Placebo	2.0
REGN3500 100 mg SC Q4W	2	Placebo	1.0
		Placebo	2.0
REGN3500 30 mg SC Q8W	2	Placebo	1.0
		Placebo	2.0
Placebo SC Q2W	2	Placebo	1.0
		Placebo	2.0

Dose Regimen	Injections During Visit	Study Drug Administered	Injection Volume (mL)
Weeks 4 (Visit 4) and 12 (Visit 8)			
REGN3500 300 mg SC Q2W	2	REGN3500	1.0
		REGN3500	2.0
REGN3500 300 mg SC Q4W	2	REGN3500	1.0
		REGN3500	2.0
REGN3500 100 mg SC Q4W	2	REGN3500	1.0
		Placebo	2.0
REGN3500 30 mg SC Q8W	2	Placebo	1.0
		Placebo	2.0
Placebo SC Q2W	2	Placebo	1.0
		Placebo	2.0

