SC: subcutaneous; Q2W: every 2 weeks; Q4W: every 4 weeks; Q8W: every 8 weeks.

Note: All patients will receive Q2W SC injections. For the REGN3500 300 mg SC Q4W group, REGN3500 100 mg SC Q4W group, and REGN3500 30 mg SC Q8W group, there will be SC injection(s) of placebo in between REGN3500 doses so the injection frequency will match the other 2 groups (REGN3500 300 mg SC Q2W and placebo SC Q2W)

Instructions on dose preparation and administration are provided in pharmacy manual.

Subcutaneous injection sites should be alternated among the different quadrants of the abdomen (avoiding navel and waist areas), upper thighs, and upper arms, so that the same site is not injected for 2 consecutive visits. During the same dose administration, each injection must be given in a different anatomical location (eg, 1 injection administered in the right lower quadrant of the abdomen, another in the left lower quadrant of the abdomen, etc). To allow for adequate assessment of possible injection site reactions (ISRs), study drug should be administered only into areas of normal-looking skin. Instructions for recording and reporting ISRs will be provided in the study reference manual/site binder or file.

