10.4.4.4. Treatment Compliance

The compliance with protocol-defined investigational product will be calculated as follows:

Treatment compliance=

$$\frac{(\text{number of investigational product injections during exposure period})}{(\text{number of planned investigational product injections during exposure period})} \times 100\%$$

The treatment compliance will be presented by specific ranges for each treatment group. The ranges of interest will be specified in the SAP.

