2.1. Study Design and Randomization

This is a phase 2b, randomized, double-blind, placebo-controlled, parallel-group, dose-ranging study investigating the efficacy, safety, and PK profiles of REGN3500 administered to adult patients with moderate-to-severe AD. Eligible patients must have a documented history of inadequate response or intolerance to treatment with topical AD medications. This study is intended to provide information regarding 4 different REGN3500 monotherapy dosing regimens. Each REGN3500 dosing regimen will be compared with placebo to enable robust assessment of efficacy and safety.

The study duration is up to 41 weeks, including an up to 5-week (ie, 35 days) screening period, 16-week double-blind treatment period, and 20-week post-treatment follow-up period.

Approximately 300 subjects (60 subjects per treatment group) will be recruited and randomized from approximately 60 sites. Approximately 10% of patients are planned to be enrolled in Japan; and that the Japanese patients will be randomized in 2 cohorts: a sentinel cohort of 15 patients and a second cohort of 15 patients. The randomization scheme and procedure of the Japanese patients will be the same as the rest of the patients. Independent Data Monitoring Committee will review of safety data from the first 15 Japanese patients when the 15th patient completes the Day 15 visit.

Figure 1: Study Flow Diagram

D: day; EASI: Eczema Area and Severity Index; EOS: end-of-study; EOT: end-of-treatment; Q2W: every 2 weeks; Q4W: every 4 weeks; Q8W: every 8 weeks; R: randomization; W: week

On 12 February 2020, the Sponsor decided to stop the study. At that time, 129 subjects had been randomized including 6 Japanese patients. The sponsor instructed the investigators to transition all patients in the treatment phase to the twenty-week safety-follow-up period. These patients will stop the treatment and finish the end of treatment assessments before entering into the follow-up period. All patients who were in the screening period, but had not received study investigational medicinal product (IMP), will be screen failed for the reason of sponsor decision to discontinue study.

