5.6.2. Treatment Exposure and Observation Period

The duration of treatment exposure during the study in days is calculated as:

$$\text{(Date of last study drug injection - date of first study drug injection)} + x \text{ days}$$
, where x days are 7, 14, 28, 56 days for QW, Q2W, Q4W, and Q8W, respectively.

The calculations are regardless of temporary dosing interruption. The duration of exposure during the study will be summarized by treatment group using number of patients, means, SD, minimums, Q1, medians, Q3 and maximums.

In addition, the duration of exposure will be summarized categorically by counts and percentages for each of the following categories and cumulatively by these categories as well: ≥ 15 days, ≥ 29 days, ≥ 43 days, ≥ 57 days, ≥ 71 days, ≥ 85 days, ≥ 99 days, and ≥ 113 days.

The duration of observation period during the study in days is calculated as:

$$\text{(Date of the last visit - date of the first study drug injection)} + 1.$$

The number (%) of patients with observation periods will be presented by specific time periods. The time periods of interest are specified as: < 15 days, ≥ 15 days, ≥ 29 days, ≥43 days, ≥ 57 days, ≥ 71 days, ≥ 85 days, ≥99 days, ≥113 days, ≥141 days, ≥169 days, ≥197 days, ≥225 days and ≥253 days. Since the Sponsor stopped the study, it is possible that no patient reaches some time categories. If so, these categories will not be reported.

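### SAP 5.6.1 puts injections *taken* in the compliance denominator, so compliance is about 100% whatever was missed; deleting the word is not enough if the SAP 5.6.2 exposure tails set the counting period

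*SAP*

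**What the plan says.** Protocol 10.4.4.4 defines compliance as injections given divided by "number of planned investigational product injections during exposure period", and leaves only the reporting ranges to the SAP. Protocol 10.4.4.3 defines duration of exposure as last minus first injection date plus 14 days, in every arm.

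SAP 5.6.1 changes the denominator to "Number of planned study drug injections taken during exposure period" and reports two classes, below 80% and 80% or above. SAP 5.6.2 changes the addition after the last injection: "where x days are 7, 14, 28, 56 days for QW, Q2W, Q4W, and Q8W, respectively". SAP 1.2.4, which lists departures from the protocol's statistical section, mentions neither change.

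On dosing, the note to Protocol Table 1 says "All patients will receive Q2W SC injections", with placebo given between active doses. Protocol 7.1 uses study drug for both products: "Study drug (REGN3500, REGN3500-matching placebo) will be prepared by an unblinded pharmacist".

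On the early stop, SAP 2.1 reports 129 patients randomized when the sponsor stopped the study, and says of those still in the treatment phase: "These patients will stop the treatment and finish the end of treatment assessments before entering into the follow-up period".

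**The concern.** A planned injection that was taken is an injection given, so the SAP's numerator and denominator count the same thing. The ratio cannot detect a missed dose, and the 80% cut has nothing to separate.

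A programmer who sees this and drops *taken* meets a second difficulty. The formula counts over an exposure period that SAP 5.6.1 does not define. The only exposure interval nearby is the 5.6.2 duration, whose tail follows the active-dose interval, while injections are scheduled every 2 weeks in all arms. Visits that never came due because the sponsor stopped dosing could then enter the denominator as missed, in the Q4W and Q8W arms in particular. SAP 5.7 says many patients had not reached week 16 at termination, so truncated courses are common.

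At stake is whether the compliance table describes adherence and can be compared across arms.

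**Working it through.** The documents state no compliance percentage, so there is no figure to reproduce.

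**Inputs**
- Injections per visit: 3 on day 1 and at week 8; 2 at weeks 2, 4, 6, 10, 12 and 14 (Protocol Table 1; the synopsis gives the placebo regimen as "3 injections of REGN3500-matching placebo on day 1 and week 8; and 2 injections of REGN3500-matching placebo administered SC" at those six visits). Total in every arm: 2×3 + 6×2 = 18.
- Nominal dosing days: 1, 15, 29, 43, 57, 71, 85, 99, each later visit ±3 days (Protocol Table 2).
- Tail x: 14, 28 or 56 days for Q2W, Q4W, Q8W (SAP 5.6.2); 14 days in every arm (Protocol 10.4.4.3).

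**Step 1: literal SAP formula.** Compliance = injections given / planned injections that were given = 100%, or more only if unplanned extra injections were given. Take a patient dosed through week 14:
- Missed weeks 4 and 10: 18 − 2 − 2 = 14 given. SAP 14/14 = 100%; protocol 14/18 = 77.8%.
- Missed weeks 8 and 12: 18 − 3 − 2 = 13 given. SAP 13/13 = 100%; protocol 13/18 = 72.2%.

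**Step 2: *taken* ignored, 5.6.2 duration as the counting period.** D = (last injection day − first injection day) + x. The denominator is the planned injections, active and placebo, on nominal days 1 to D. The patient misses nothing up to the last dose, and visits after the stop still count as planned.

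Example, Q8W, last dose week 4: D = (29 − 1) + 56 = 84. Visits on days 1, 15, 29, 43, 57 and 71 fall inside: 3+2+2+2+3+2 = 14 planned. Given: 3+2+2 = 7. Compliance 7/14 = 50%.

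| Last dose | Q2W, placebo | Q4W | Q8W |
|---|---|---|---|
| Day 1 | 3/3 = 100% | 3/5 = 60.0% | 3/9 = 33.3% |
| Week 2 | 5/5 = 100% | 5/7 = 71.4% | 5/12 = 41.7% |
| Week 4 | 7/7 = 100% | 7/9 = 77.8% | 7/14 = 50.0% |
| Week 6 | 9/9 = 100% | 9/12 = 75.0% | 9/16 = 56.3% |
| Week 8 | 12/12 = 100% | 12/14 = 85.7% | 12/18 = 66.7% |
| Week 10 | 14/14 = 100% | 14/16 = 87.5% | 14/18 = 77.8% |
| Week 12 | 16/16 = 100% | 16/18 = 88.9% | 16/18 = 88.9% |
| Week 14 | 18/18 = 100% | 18/18 = 100% | 18/18 = 100% |

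**Step 3: protocol tail.** With x = 14 in every arm, the same patient scores 100% at each nominal last-dose week in all five arms. For the Step 2 example, D = 28 + 14 = 42 and compliance is 7/7.

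**Step 4: active injections only.** The SAP 5.6.1 lead-in says compliance is calculated for REGN3500 injection.
- Active injections set both the count and the period: 100% at every stop in the active arms, and 0/0 for placebo.
- Active injections set the count, but the period runs from the last injection of any kind: Q4W scores 1/2, 2/3 and 3/4 after weeks 2, 6 and 10; Q8W scores 1/2 after weeks 2, 4 and 6; otherwise 100%.

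**Step 5: visit windows.** Suppose a Q2W patient's week 2 dose is given on day 18, inside the ±3-day window, and is the last. D = (18 − 1) + 14 = 31, which takes in nominal day 29: 5/7 = 71.4%. The clean 100% column for Q2W and placebo therefore holds on nominal days only.

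**The case against.** The best case for the plan is that the second part rests on readings the SAP does not state. SAP 5.6.2 defines a duration for summary tables and does not call it the exposure period. SAP 3.2 separately defines a treatment period, which for sponsor-stopped patients with neither a week 16 nor an early termination visit ends on 12 February 2020. Nothing says that injections scheduled after the stop remain planned. The 5.6.1 lead-in leaves room for an active-only count, which can give 100% throughout the active arms. All of this stands, and it makes the percentages in Step 2 conditional. Counting placebo is nonetheless the better supported reading: Protocol 7.1 defines study drug that way, and an active-only count leaves placebo undefined.

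The consequence is also small. SAP 1.1 makes all analyses descriptive, an abbreviated report is planned, and compliance defines no analysis set. SAP 5.6.1 also requires the number of doses and a per-dose listing, and SAP 5.5 gives reasons for discontinuation, so a careful reader could tell a sponsor stop from missed doses. That limits the damage but does not make the table correct.

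A reader might infer that sponsor-stopped Q4W and Q8W patients in general would be classed below 80%. The documents do not support that. Even under the least favourable reading, Q4W patients last dosed at week 8 or later score 86 to 100%, and Q8W patients last dosed at week 12 or later score 89 to 100%. Nor can the two defects occur together: if *taken* is applied, nobody falls below 80%.

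**Conclusion.** The denominator in SAP 5.6.1 is wrong as written. It departs from the protocol without being listed as a change and, followed literally, gives about 100% for every patient. This part needs no assumption beyond the wording.

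The second part is conditional. It requires that *taken* be ignored, that the exposure period be the 5.6.2 duration, that placebo injections count, that visits after the stop count as planned, and that nominal days apply. A fully adherent patient then scores below 80% only if the last dose was at week 6 or earlier (Q4W) or week 10 or earlier (Q8W).

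Last-dose weeks by arm are not given, so the number affected among the 129 cannot be computed, and no claim can be made that apparent non-compliance would in fact concentrate in the lower-frequency arms. What can be said is that the same fully adherent patient could be reported anywhere from 33% to 100% depending on the reading chosen, so the output is not pre-specified. The effect is confined to one descriptive table; no efficacy or safety conclusion depends on it. The text should still be corrected, because the correction is cheap.

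**What to change.** In SAP 5.6.1:
- Delete *taken*.
- Define the denominator as all planned study drug injections, REGN3500 and matching placebo, at dosing visits from day 1 to week 14 that came due before permanent discontinuation or the sponsor stop.
- Count a visit as due if it was dosed, or if its +3-day window closed before the stop date. A visit on or after the stop date is then not counted as missed. Counting simply through the stop date would bring the fault back: a patient fully dosed through week 6 and stopped at the week 8 visit would score 9/12 = 75%, where this rule gives 9/9.
- State that the 28-day and 56-day tails of 5.6.2 are not used for compliance.
- Reword the lead-in so that it agrees with the formula on which injections count.

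List the change from the protocol in SAP 1.2.4. The missed-dose patient in Step 1 keeps 14/18 = 77.8%, so the rule still detects missed doses. The cost is a few lines of SAP text and one derivation to reprogram; no new data are needed.
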